#### STATEMENT OF COMPLIANCE

This document is a protocol for a clinical research study. The study will be conducted in compliance with all stipulations of this protocol, the conditions of ethics committee approval, the NHMRC National Statement on Ethical Conduct in Human Research (2007) and the Note for Guidance on Good Clinical Practice (CPMP/ICH-135/95).

# List of abbreviations:

ADR	Adverse Drug Reaction
AE	Adverse Event
ALP	Alkaline phosphatase
ALT	Alanine aminotransferase
AST	Aspartate aminotransferase
CRF	Case Report Form
CSDP	Centers for Social Disease Prevention
ECP	Expert Clinical Panel
eCRF	Electronic Case Report Form
Eos	Eosinophils
FBC	Full Blood count
GCP	Good Clinical Practice
GGT	Gamma-Glutamyl Transferase
Hb	Haemoglobin
HIV	Human Immuno-deficiency Virus
ICH	International Council for Harmonization of Technical Requirements for Pharmaceuticals for Human Use
LTBI	Latent Tuberculosis Infection
MCV	Mean corpuscular volume
MTB	Mycobacterium Tuberculosis
Neut	Neutrophils
NTP	National Tuberculosis Program
PCF	Participant consent form
PIS	Participant Information Statement
RCT	Randomized Controlled Trial
SAE	Serious Adverse Event
ТВ	Tuberculosis
TST	Tuberculin skin test
ULN	Upper limit of normal
WCC	White cell count
WHO	World Health Organization

# **Project overview**

Title: Test and Treat to End TB

Duration: Four years (2021 to 2025)

# 1) Synopsis

This study is community-based cluster-randomised controlled trial of universal testing and treatment for latent TB infection, together with active case finding for TB disease, to reduce the prevalence of TB disease.

The **primary objective** of the study is to estimate, among people aged 15 years and over living in Ca Mau Province, southern Vietnam, the effect of universal testing for and treatment of latent TB infection, together with active case finding for TB, on the population prevalence of bacteriologically-confirmed TB two years after the intervention.

#### The secondary objectives are

- 1. To estimate the incidence of severe adverse events attributable to the intervention;
- 2. To estimate the effect of the intervention on all-cause mortality;
- 3. To estimate the costs and cost effectives of the intervention.
- 4. To estimate the prevalence of latent TB infection four years after the intervention among children born between 2008 and 2016,

This **design** is an open-label, parallel-group, cluster-randomised controlled trial. The **study population** is people living in Ca Mau Province, Vietnam. The **intervention** is universal testing for, and treatment of, latent TB infection combined with active case finding for TB. The **comparison** is usual care, that is, routine detection of TB cases based on self-presentation of symptomatic people to healthcare facilities. The **primary outcome** is the population prevalence of TB two years after the intervention.

# 2) Background

# Global burden of tuberculosis and global goals and targets

Every year, more people die due to tuberculosis (TB) than any other infectious disease. TB is one of the top 10 causes of death worldwide (1). This is in spite of the fact that we have had tests to diagnose both active disease and the presence of TB infection for more than a century, as well as effective anti-TB drugs for more than half a century. Hence, it is extraordinary that in 2019, 10 million people developed the disease, nearly 2 million people will die from TB and 2 billion people remain infected with M. *tuberculosis* (1).

The United Nations' Sustainable Development Goal 3 ("Ensure healthy lives ...") includes a target of ending the TB epidemic by 2030. WHO have set ambitious targets to END TB by the 2035, including reducing deaths by 95% and incident cases by 90% compared with 2015 levels (2). However, currently, it is estimated that the current global annual rate of decline in TB incidence is 2.3% per annum (1), which is far lower than the 10% decline required to achieve the 2035 target (3). We are not on track to achieve these targets on present trends.

## Limitations of existing approaches and of some alternatives

The long-standing dominant global strategy for TB control has enhanced passive case finding and treatment at its core. This strategy focuses on improving access to TB diagnosis, treatment and care to ensure that patients who have TB disease are diagnosed and treated appropriately when they present with symptoms of TB. Although there have been substantial gains in TB control in some rapidly developing, middle income countries (particularly in China) (4), the decline in incidence of TB has been exceedingly slow in many high TB burden countries and the prevalence remains very high (5\*), ensuring ongoing transmission of TB infection. Barriers to the implementation of the current strategy include health system weakness, particularly in primary care (6), and the fact that many patients with pulmonary TB do not report typical or diagnostic symptoms (5\*) or delay seeking treatment due to the indolent nature of the disease and due to social stigma (7). As a consequence, a significant proportion of new TB patients (2.9 million in 2019 (1)) are not diagnosed and treated. Although economic development and health system strengthening will lead to a decline in TB burden in many countries (6), at the present rate of progress this will take many decades (3). Consequently, the high burden of TB will continue, with little progress towards targets, despite substantial ongoing investment in TB control programs (8).

Considerable resources and hopes have been invested in the development of new drugs, to shorten the duration of treatment, and new vaccines to prevent infection, progression or reactivation (3). Sadly, while new drugs have been developed for management of TB that is resistant to the existing first- and second-line drugs, the much anticipated blockbuster drugs for drug-susceptible TB and vaccines (9) have not eventuated and will not arrive in time to achieve these targets.

# Rationale for community-wide active case finding

Reducing the pool of prevalent infectious cases of pulmonary TB by finding and treating as many cases as possible, as early as possible, and reducing ongoing transmission of TB is key to controlling the epidemic (3). Active case finding, in which people not seeking health care for symptoms of TB are invited to be screened for TB

disease, has played an important role in TB control in higher income settings since before the anti-tuberculous chemotherapy era. There was a dramatic decline in mortality due to TB in North America and in Britain coinciding with the introduction of community-wide mass radiography and anti-tuberculous antibiotics during the 1950s (10-12). In Alaska, community-wide screening, accompanied by treatment of latent TB infection, was associated with a steep reduction in TB incidence, which was maintained over decades (13). Mass radiography screening was also widely implemented in Australia around this time (14), coinciding with a period of rapid decline in TB incidence and mortality in this country.

There have been some attempts to implement active case finding in high-burden countries (15, 16). These have mainly focused on screening high-risk subsets of the population, primarily known contacts of people with active TB. Indeed, we have recently shown, for the first time in a highly endemic setting, that active case finding in household contacts of patients with TB increases detection of smear positive (infectious) cases 6.4 fold compared to standard care (17\*). However, despite this high yield of contact tracing (18\*), most newly identified cases of TB in highly endemic settings are not recognised as contacts of patients who have been diagnosed with TB (19), implying that most transmission occurs outside this context. Similarly, most people with TB do not belong to other identified high-risk groups (such as, prisoners, illicit drug users or people with diabetes). Apart from sub-Saharan Africa, most people with TB do not have HIV infection. In fact, most cases and deaths due to TB occur in south and south-east Asia, where the prevalence of HIV is low. Hence, the impact of targeted active case finding in high-risk groups on the pool of prevalent cases of TB, and consequently on ongoing transmission within the whole population, will be relatively small (20). Therefore, in high burden settings, it will be necessary to screen the entire population and treat all, or nearly all, prevalent cases to reduce transmission (21). By interrupting transmission from cases with infectious TB, only cases resulting from reactivation of latent infection will occur.

[figure not shown]
## A new approach to active case finding

Historically, mass chest radiography has been used as a community-wide screening tool in high-income settings (10). It has also been used in low-middle income settings to conduct TB prevalence surveys (e.g., 5\*). However, problems with infrastructure and logistics, human resources, cost, and radiation exposure all limit the utility of radiography as a tool for repeated community-wide screening in low-income and remote settings.

The availability of a fully automated rapid nucleic acid amplification test for diagnosis of TB (Xpert® MTB/RIF, Cepheid, Sunnyvale, CA) has several advantages as a potential screening tool. It is suitable for operation at district-level facilities with a minimal level of training and technician handling of specimens and has a turn-around-time of less than 2 hours. There is no requirement for a biosafety cabinet. This test has been rapidly adopted as a diagnostic tool in low and middle-income countries (22). We have shown that it has very high specificity (23\*). A recent enhanced version (Xpert® MTB/RIF Ultra, Cepheid) has improved sensitivity and similar specificity (24).

We have recently completed a cluster-randomised controlled trial of active case finding

for TB in Ca Mau, a province of Vietnam ("ACT3", 23\*). Residents of 60 active intervention clusters (n =  $\sim$  50,000 adults) were subjected to annual screening for pulmonary TB for three years. Screening involved collecting spontaneously expectorated sputum from all adults, regardless of symptoms. These sputum specimens were tested using Xpert MTB/RIF. Participants who screened positive were secondarily

evaluated by chest xray and sputum mycobacterial culture. Those in whom TB was confirmed received treatment through the National TB Program. There was no intervention in the control clusters, where passive case detection continued. The primary study endpoint was the prevalence of pulmonary TB disease in persons aged 15 years and over in the fourth year of the study.

The study demonstrated a 44% lower prevalence of TB disease among adults (figure) and a 50% lower prevalence of TB infection (positive interferon gamma release assay) among children aged 6 to 14 years in the actively screened clusters, compared with the control clusters at the conclusion of the study(25). This study provides strong preliminary evidence for an effective intervention for TB control.

# Rationale for "universal test and treat" approach to latent TB infection

Although we have shown that active case finding is effective in substantially reducing the prevalence of TB, we recognise that it will not be sufficient to eliminate TB. This is because of the large pool of people who are latently infected with TB. Indeed, we have shown, in Ca Mau, Vietnam, that 38% of adults have latent TB infection (26\*). This large cohort of individuals represents a reservoir from which new cases of active TB, with consequent ongoing transmission, will continue to arise for decades to come (27\*, 28). Hence, as the late eminent U.S. TB researcher, George Comstock, recognised many years ago (13, 29), ending TB in high burden countries will require widespread treatment of latent TB infection in the general population. This proposal investigates how to achieve this, at scale and in a sustainable manner, in a setting endemic for TB.

[figure not shown]
# New tools that make this new approach more feasible

Until recently, the standard treatment for latent TB infection was isoniazid administered daily for six to nine months. The demonstration that a 12-dose, once weekly regimen (3HP) comprising isoniazid and rifapentine is as effective in preventing TB, has better adherence and is better tolerated than nine months of isoniazid in adults and children with latent TB infection (30) has made the prospect of supervised, large-scale, community-based treatment campaigns more feasible. Such a treatment campaign could be considered analogous to multi-dose vaccination campaigns.

## Modelling the cost-effectiveness of "universal test and treat"

We have implemented a TB transmission model with seven population categories representing TB states (31) calibrated to Vietnam-specific demographic and epidemiological data. We assumed that 80% of people would consent to be screened for latent TB infection and that the efficacy of treatment in reducing reactivation of latent TB infection was 60%. The cost of a course of treatment (3HP) was assumed to be US\$50. Our preliminary findings, summarised in the adjacent figure, are that the proposed universal test and treat intervention is highly cost-effective with an incremental cost-effectiveness ratio (ICER) of US\$170 per QALY gained over a 10-year time horizon. Over a 30-year time horizon the intervention is predicted to cost

50 <\$US per QALY gained and if the price of rifapentine can be reduced below \$US 18 per course, the program is predicted to be cost-saving to the government of Vietnam over a time horizon of 10 years. In this study we will acquire data on effectiveness and costs that will enable better quality estimates of costeffectiveness.

# 3) Aim and hypothesis

The **overall goal** of this project is to acquire and present the evidence that will underpin a transformation in the global approach to TB elimination in low and middle-income countries with a high burden of TB.

**Hypothesis:** That universal testing and treatment for latent TB infection, added to active case finding for TB disease, will reduce the prevalence of TB by at least 75% after 2 years.

We also hypothesise that this intervention will be highly cost effective within a 10-year time horizon and will be cost saving within a 20-year time horizon.

# 4) Objectives

The **primary specific objective** is to estimate, among people aged 15 years and over living in Ca Mau, southern Vietnam, the effect of universal testing and treatment of latent TB infection, together with active case finding for TB, on the population prevalence of bacteriologically-confirmed TB two years after the intervention.

#### The secondary objectives are

- 1. To estimate the incidence of severe adverse events attributable to the intervention;
- 2. To estimate the effect of the intervention on all-cause mortality;
- 3. To estimate the costs and cost effectiveness of the intervention.
- 4. To estimate the prevalence of latent TB infection four years after the intervention among children born between 2008 and 2016,

# 5) Outcome – primary endpoint

The primary endpoint is the prevalence of bacteriologically confirmed pulmonary TB, as assessed two years after the intervention. A **prevalent case of bacteriologically confirmed pulmonary TB** will be defined as a study participant whose sputum tests positive for MTB on Xpert Ultra.

Sensitivity analyses will be conducted using alternative definitions based on clinical, radiological and additional microbiological (culture) data.

# 6) Study Design

[figure not shown]
# Study setting and population

Vietnam has a nationally administered, centralised TB control program administered by the National TB Program. Most TB cases are diagnosed and managed at district level, where the diagnosis of pulmonary TB is based on sputum smear microscopy for people presenting with symptoms of TB. The standard treatment regimen for TB is oral isoniazid, rifampicin, pyrazinamide, and ethambutol for two months followed by isoniazid, rifampicin and ethambutol for four months.

The study will be conducted in Ca Mau, the southern-most province of Vietnam, which has a population of 1,216,400 people living in 101 communes within nine districts. In 2017, there were 1,045 reported cases of pulmonary TB in Ca Mau. Multi-drug resistant (MDR) TB (n=21, 2.0% in 2017) and HIV co-infection (n=19, 1.8% in 2017) are both relatively uncommon in Ca Mau. After our recent RCT in Vietnam (17\*), active case finding in household contacts is being scaled up and is being established in Ca Mau under the direction of AI [name] and CI [name].

# Trial design

The study participants will be the residents of randomly selected clusters in the province of Ca Mau. Clusters, which are defined sub-communes, will be randomly assigned to active and control status at baseline. There will be no measurements at baseline. People aged five years and older living in active intervention clusters will be screened, and where appropriate treated, for active and latent TB at baseline. All people in the control clusters will have routine care for detection and treatment of TB, with no active study intervention. The primary study endpoint, the prevalence of bacteriologically-confirmed pulmonary TB, will be assessed in people aged 15 years and over, two years after the intervention, using community-wide active case finding in both intervention and control clusters. The primary comparison will be between the primary endpoints in the active intervention and control arms.

# 7) Selection of study population

## **Cluster selection**

Clusters are sub-communes (known as 'Åp', roughly equivalent to a village, suburb or hamlet) with an average population of ~ 1,000 persons aged 15 years and over. Sub-communes are grouped in communes, which are grouped in districts. There are 946 sub-communes among the 101 communes in Ca Mau. In ACT3 (see page 9) we screened 120 sub-communes (~90,000 people) for TB on one or four occasions. These sub-communes will be excluded from participation in the present study. From the remaining 826 sub-communes we will randomly select the required number of clusters stratified by district and with a probability proportional to population size.

## Cluster allocation to treatment groups

The selected clusters will be randomly assigned to active intervention and control status, again stratified by district and by population size (32). This will ensure both representative selection and balanced allocation of clusters from within the province.

## Eligibility for the intervention

All enumerated residents of the sub-communes selected and randomized to the intervention arm will be assessed for eligibility in two phases: initially, they will be assessed for eligibility for the testing phase and, subsequently, those who have consented to this phase will be assessed for eligibility for the treatment of LTBI phase.

In each phase, individuals will only be included if they have given written informed consent to participate in that phase of the study.

All enumerated residents of the sub-communes selected and randomized to both the intervention and control arms will be assessed for eligibility for the prevalence survey (endpoint evaluation) two years after the intervention.

#### **Eligiblity criteria for testing phase**

1. Aged 5 years or older on the date of enumeration; AND

- 2. Capable of giving informed consent or, if aged < 15 years, having a parent or guardian who can give consent. Assent will also be routinely sought from children aged 10 to <15 years; AND
- 3. Not currently taking treatment for tuberculosis.

### **Eligibility criteria for treatment of LTBI phase**

- 1. Meet eligibility criteria for testing and consented to screening; AND
- 2. Tuberculin skin test (TST) reaction size  $\geq$  10mm (or > 0mm if known to be HIV +ve) AND
- 3. Either no abnormality consistent with TB on chest radiograph OR abnormal radiograph but two sputum specimens are culture negative for *M. tuberculosis*
- 4. Not pregnant or planning to be pregnant in next 6 months
- 5. No important potential drug interactions with the intervention regimen, defined by attending medical officer in accordance with a schedule.
- 6. No known allergy or hypersensitivity to the active substance or any of the ingredients of the study drugs
- 7. Has not completed a course of treatment for TB within the preceding two years.
- 8. Serum transaminases (AST and ALT) are both < 3 x upper limit of normal
- 9. No severe or life-threatening illness that is considered by the attending medical officer to make treatment for LTBI inappropriate.

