# Household visit 48-96 hours after TST injection

Field workers will return to the household 48-96 hours after placement of the TST to read the size of the induration. The induration will be digitally photographed and measured (perpendicular to the long axis of the forearm) using the 'ballpoint technique. pen' Callipers will be used to measure the size of the reaction. Reactions > 10mm (or > 0mm for participants known to be HIV +ve) will be classified as

positive. ("Tuberculin test forms - placement and reading").

Screened participants who have a positive TST or who report symptoms of TB will be asked to:

- 1. Provide a single, spontaneously expectorated sputum specimen, if possible. The study team member will explain how to expectorate sputum using a pictorial guide. All sputum specimens will be transferred in a foam-insulated cool box to our laboratory in Ca Mau City (see "Sputum Xpert form"). At the laboratory, specimens will be tested using Xpert MTB/RIF Ultra, or equivalent test, within 48 hours of collection. If the initial Xpert test is reported as "invalid", the test will be repeated.
- 2. Provide information on concomitant medications taken in the past seven days or planned to take in the next seven days, and on presence of known liver disease or HIV infection, drug allergy and consumption of alcohol will be acquired using a questionnaire (see "Pre-treatment Assessment Form fieldworker"). The fieldworker will consult with the study medical officer if the participant reports he / she is taking any medication. The participants will not be required to cease any of their current medications to participate in this study.
- 3. In addition, women aged 15-45 years will be asked if they are pregnant or are attempting to fall pregnant or are breastfeeding (see "Pregnancy and lactation screening form").

Patients who report that they are HIV +ve and have TST reaction > 0mm will be referred to the HIV program for further management.

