#### TB preventive treatment in those with LTBI but without active TB

Participants who meet **all** of the following criteria will be eligible for treatment for LTBI:

- Are aged  $\geq$  5 years and have consented to the screening phase; AND
- Have a TST  $\geq$  10 mm (and are not known to be HIV +ve); AND
- Are not excluded from 3HP regimen by the pregnancy or lactation screening questionnaire; AND
- Have not completed a course of treatment for TB within the preceding two years; AND
- Do not have a history of allergy or known hypersensitivity to any of the study drugs; AND
- Do not have active TB according to the following criteria:
  - 1. Expectorated sputum tested negative for MTB on GeneXpert or did not produce a sputum specimen for Xpert testing **AND** have a chest x-ray that was not reported as "consistent with TB" **OR**.
  - 2. Did not have a chest radiograph **BUT** have two sputum specimens that both tested negative for MTB on GenXpert **OR**
  - 3. Have a chest x-ray that was reported as "consistent with TB" **BUT** have two sputum cultures that have been reported as negative for TB and any GeneXpert tests (if collected) are negative for TB.

will be recommended for further assessment for treatment of LTBI by field worker.

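### The section 7 list of who may receive preventive treatment contradicts the section 8 list on known HIV infection and on people without a chest film, and omits two exclusions that section 8 applies

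*Protocol*

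**What the plan says.** Protocol section 7, under Eligibility criteria for treatment of LTBI phase, gives nine numbered criteria.

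- Item 1 carries forward the testing-phase criteria, one of which is not being on TB treatment.
- Item 2 sets the tuberculin threshold at "10mm (or > 0mm if known to be HIV +ve").
- Item 3 excludes active TB by film and culture: "Either no abnormality consistent with TB on chest radiograph OR abnormal radiograph but two sputum specimens are culture negative for" *M. tuberculosis*.
- Item 4 covers pregnancy, current or planned, and does not mention breastfeeding.

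Protocol section 8, under TB preventive treatment in those with LTBI but without active TB, gives a second list and says that people who meet all of it will be eligible.

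- Its skin-test line reads "10 mm (and are not known to be HIV +ve").
- It offers three routes for ruling out active TB. The first needs a film not reported as consistent with TB and "Expectorated sputum tested negative for MTB on GeneXpert or did not produce a sputum specimen for Xpert testing". The second is for people who had no film but "have two sputum specimens that both tested negative for MTB on GenXpert". The third is for people with a TB-consistent film who "have two sputum cultures that have been reported as negative for TB and any GeneXpert tests (if collected) are negative for TB".
- It also requires that participants "Are not excluded from 3HP regimen by the pregnancy or lactation screening questionnaire".

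Other parts of section 8 agree with this second list. Under Household visit 48-96 hours after TST injection: "Patients who report that they are HIV +ve and have TST reaction > 0mm will be referred to the HIV program for further management". The subsection on pregnant and breastfeeding women rules out latent TB treatment for breastfeeding women.

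**The concern.** Both lists answer the same question, namely who may be given weekly isoniazid and rifapentine, and neither refers to the other. For some people they give opposite answers. The formal eligibility list is what an ethics committee, an auditor or a trainer would normally take as the rule. Here it admits a group that the working procedures send elsewhere, and it has no place for a group that the working procedures admit.

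Three things depend on having one list. Staff training covers eligibility criteria. Protocol deviations must be notified to the ethics committee, and treating a person without a film follows section 8 but departs from section 7. Item 5 of the indications for cessation stops treatment on onset of a condition that would have made the participant ineligible. If HIV infection becomes known during treatment, the section 8 list says stop and the section 7 list does not.

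**Working it through.** No sample size or power figure is involved. The check sets the two lists side by side and passes the same person through each, with all other criteria met.

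| Profile | Section 7 list | Section 8 list |
|---|---|---|
| Reference: HIV not known, TST 12 mm, film not TB, Xpert negative | yes | yes |
| Reference: as above, but TB-consistent film and two negative cultures | yes | yes |
| Known HIV-positive, TST 5 mm, film not TB, Xpert negative | yes | no |
| Known HIV-positive, TST 12 mm, film not TB, Xpert negative | yes | no |
| TST 12 mm, no film, two Xpert-negative specimens | no | yes |
| TST 12 mm, film not TB, Xpert positive, not on TB treatment | yes | no |
| TST 12 mm, TB-consistent film, two negative cultures, Xpert positive, not on TB treatment | yes | no |
| Breastfeeding, TST 12 mm, film not TB, Xpert negative | yes | no |

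The six discordant rows reduce to four points, of two kinds.

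**Direct contradictions.**

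1. *Known HIV.* Section 7 is not merely silent. It sets a specific, lower threshold for people whom section 8 excludes. The two HIV rows are this one conflict at two reaction sizes.
2. *No film.* A person without a radiograph meets neither alternative in item 3 of section 7, but meets the second route in section 8. Here section 7 is the stricter list, so it is not simply a looser summary that section 8 narrows.

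**Omissions from section 7.**

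3. *Positive Xpert.* Item 3 of section 7 has no Xpert condition. Item 1 narrows the gap, because a person already on TB treatment fails the testing-phase criteria that it carries forward. What remains is an Xpert-positive person whose TB is not confirmed or who has not started treatment. Section 8's subsection on abnormal films and positive Xpert tests sends such people for evaluation, but its explicit bar on latent TB treatment names only those with a TB-consistent film. For an Xpert-positive person with a clear film, the stated bar is in the section 8 list. The two Xpert rows are this one omission with two film results.
4. *Breastfeeding.* The exclusion appears only in section 8.

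The reverse gap is not counted. Section 7's items on drug interactions, transaminases and severe illness (5, 8 and 9) are absent from the section 8 list, but the Medical Review subsection applies them.

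The protocol does not give the number of people affected. Its only HIV figure is 19 co-infected among 1,045 reported pulmonary TB cases in Ca Mau in 2017: 19 / 1,045 = 1.8%. That describes TB patients, not residents with a positive skin test, and cannot be turned into a count here.

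**The case against.** The strongest reply is that section 8 settles the matter in practice. Consent for treatment is sought from people eligible under the criteria just above it, which is the section 8 list, and HIV-positive reactors are expressly referred elsewhere. This stands, and it is why the point is minor.

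A second reply is that the section 8 list is partly a triage step, since it closes by having the field worker recommend such people for further assessment, and that section 7 only presupposes a film without stating a bar. This has some force for the no-film route. But the section 8 list also says that those who meet it will be eligible, and the consent step relies on it. Section 7 gives a person without a film no way to qualify.

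A third reply concerns consistency. If items 5, 8 and 9 are excused because another subsection supplies them, the Xpert and breastfeeding exclusions should be excused in the same way. That is fair. They are therefore described as omissions and not counted as contradictions.

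A reader might infer that the protocol would give preventive therapy to people with active TB because section 7 ignores Xpert. The documents do not support this. Xpert-positive people are sent for evaluation, those with confirmed TB are treated for TB, those on treatment fail item 1, and the section 8 list bars the rest.

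**Conclusion.** Wrong as written, and minor. The section 7 list contradicts the section 8 list on two points, known HIV infection and people without a film, and omits two exclusions that section 8 applies, a positive Xpert and breastfeeding. A reader might take the six discordant profiles as six conflicts, but they are two contradictions and two omissions.

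The expected number of people wrongly treated is small, on the assumption that field staff follow section 8, as the consent step indicates. Nor do the documents support an inference that the trial's main result is at risk. The primary analysis compares randomised clusters by intention to treat with the enumerated adult population as the offset, so it is essentially unaffected, and the sample size does not depend on these criteria. What remains is an eligibility rule, bearing on patient safety, that gives two answers with no clause to choose between them.

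**What to change.** Amend the section 7 list as follows.

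- Item 2: TST of at least 10 mm and not known to be HIV-positive; known HIV-positive people with any reaction above 0 mm are referred to the HIV program.
- Item 3: no positive Xpert result, and one of (a) a film not reported as consistent with TB, (b) no film but two sputum specimens both Xpert-negative, or (c) a film consistent with TB but two sputum cultures negative. The condition should be phrased as no positive result. A phrase such as any result negative could be read as satisfied by one negative beside one positive.
- Add an item: not breastfeeding.
- Keep items 5, 8 and 9.

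Then have the section 8 eligibility subsection, the treatment-consent paragraph and item 5 of the indications for cessation refer to this single list.

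The cost is a wording amendment. No section 8 field procedure changes, and neither does the sample size or the primary analysis.
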